Because full confidentiality regarding pregnancy cannot be entirely guaranteed, these testing requirements and the limited scope of confidentiality will be made known to all subjects during the consent procedure. In this manner, young women who would not be comfortable with pregnancy testing or sharing the results of such testing can opt out of the study at the time of the initial consent, without having to declare specific reasons.

Magnetic Resonance Imaging (MRI) Acquisition: In an MRI study, some education on the nature of the stimulus sequence, its presentation, and the response required, may be necessary. The subject is instructed to remove jewelry, wallet, and any metallic objects from their person. Baseline MRI scans will be performed at the UT-Austin BIC on a 3 Tesla (3T) Siemens VIDA scanner. The alcohol/placebo session will occur on the 3T Siemens Vida imaging system in the Dell Medical School's Health Discovery Building. The alcohol/placebo session will take place in HDB as the PI's research space is in this building and there will be comfortable and private space for participants to detox after their alcohol/placebo sessions. The 3T field strength falls within FDA limits and is now widely used clinically; the scanner also allows us to work within conventional research limits for dB/dT and SAR (the other FDA-monitored criteria related to aspects of the intensity of the MR imaging). Although this system provides the standard operating range for research, we also carefully monitor each participant for possible discomfort related to MR imaging (details are discussed in Section VI, D).

The subject is fitted with earplugs and/or headphones. The subject is positioned inside the MRI scanner, instructed to lie motionless during the procedure, and told that he/she can communicate with the operator through the intercom system and can be seen by the operator via window. The time period of the baseline MRI examination is approximately 45 minutes. Subjects can be removed at any time from the scanner by simply requesting to be. All scanning sessions include collecting anatomical images. Generally, scanning sessions include acquisition of standard localizer images to allow subsequent slice prescriptions (i.e., to find where the head/brain are positioned relative to the bore of the MRI scanner).

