Upon arriving for their session participants will receive breathalyzer tests (Also-Sensor IV Handheld Breath Alcohol Tester (Intoximeters Inc. St. Louis, MO) to ensure a .00 % breath alcohol concentration (BrAC). Participants will have their heart rate and blood pressure measured and be weighed (for purposes of beverage preparation, see below). Female participants will be required to test negative for pregnancy. The participant will be informed that the test results will be confidential. If a participant should test positive for pregnancy, a research assistant or the PI will immediately take the participant in to a private room and inform them of the test results in a sensitive manner. The participant will be informed that they should discuss the results with their doctor, and will be provided with a list of referrals should they want to discuss the impact of the results with a counselor. The participant will not be allowed to continue with the alcohol/placebo administration sessions but will be provided transportation home either by a sober friend or family member.

In an adjacent room, the participant will complete the Time Line Follow Back interview. Participants will have been fasting from food for 4 hours prior to their session, so before beginning consumption of their beverages, they will be provided with a light snack of pretzels. In addition to facilitating the participants' comfort, food intake delays the rate of alcohol absorption and increases the duration of the ascending limb of the BAC curve (when we will be conducting the MRI session). We will give participants a weight adjusted amount of pretzels based on their body weight so that they will receive 1 calorie per pound (e.g., a 150-pound participant would receive 150 calories; roughly 7 large pretzels. This has become standard practice for alcohol administration studies (e.g., [33, 34]). A gluten-free option will also be available.

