60 total participants will complete baseline assessment, alcohol and placebo sessions (30 diagnosed with bipolar disorder and 30 healthy comparison subjects). All subjects will be between 21 and 26 years of age. We plan to include equal numbers of males and females and minorities in proportions representative of the population in the greater Austin area. We expect many subjects will be students at University of Texas. We also expect to recruit approximately 10 participants who will not meet inclusion/exclusion criteria following initial clinical assessment (e.g., they do not meet criteria for bipolar disorder type I). These individuals will be compensated for completing the clinical interview but will not be invited to come in for the baseline scan or the alcohol/placebo MRI session. Total participants to be recruited includes 70 young adults.

b Minimum Age

To input text, click in the light grey area below.

21 years of age

c Maximum Age

To input text, click in the light grey area below.

26 years of age

d Inclusion Criteria

To input text, click in the light grey area below.

Eligibility will be determined by the staff consenting subjects, under the supervision of the Principal Investigator.

Inclusion Criteria:

All Subjects:

1. ages 21-26 years
2. male and female subjects from all racial and minority groups

Subjects with Bipolar Disorder:

1. diagnosis of bipolar disorder type I

7

Total Sample Size

To input text, click in the light grey area below.

Total study participants that will be recruited are 70 young adults (30 participants with bipolar disorder and 30 typically developing comparison young adults will complete the study and estimate 10 participants will not meet inclusion/exclusion criteria following initial clinical interview).

8

Sample size rationale

To input text, click in the light grey area below.

The proposed N in this study has the power to detect medium to large effects. At an alpha=0.05, 30 subjects per group will provide >80% statistical power to detect a within subject ES $d \geq 0.5$ and a between group ES $d \geq 0.7$. This compares favorably with large ESs calculated from between group differences in subjective response to alcohol in youth at risk for bipolar disorder (defined by previous hypomanic experiences; $d > 1.3$) [53]. Our design

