is sufficiently powered for both aims. In preliminary data, we observed large between group ESs when comparing differences in subjective response to alcohol (with Cohen's d ranging from 0.7 to 1.3; Aim 1a), large within group ESs when performing correlations between response to alcohol and drinking patterns (r 's ranging 0.7 to 0.9, Aim 1b), and large ESs in healthy participants (when comparing alcohol scan to baseline scan for Aim 2) with Cohen's d ranging from 0.4 to 3.3. Conversely, we observed small ESs in bipolar disorder when comparing alcohol and baseline scans (with ESs as low as 0.03). Calculated sample size required to reach significance from pilot data ranged between $N=3$ to $N=29$ across both aims. The recruitment of 30 per group through this application ensures adequate power for testing our hypothesis.

OBTAINING INFORMED CONSENT

9

Consent and Assent Processes

Provide a detailed description of the consent process including who will obtain consent, where, and when consent will occur in such a manner that participants have sufficient time for adequate consideration.

To input text, click in the light grey area below.

Subjects are consented on a 1:1 basis with the PI, co-investigators, or research associates. The staff member reads the consent form aloud with the subject. The subject is encouraged to stop the staff member and ask questions along the way. In addition, the staff member anticipates questions and describes anything that seems unclear in more detail. After reading the consent form, the subject is asked again if they have any questions. Any questions are answered. They are then asked by the staff member whether he/she wishes to participate (consent). This enhances independent decision-making by never assuming the subject automatically wants to participate after reading the consent form.

Subjects will be asked if they will permit us to stay in contact with them in order to invite them to return for the second assessment and scanning session 1-year later. There may be some subjects who may only be willing to participate in the imaging component but will not wish to give a saliva sample and choose not to participate in the genetic component. In that case they will only be consented for the interview and the imaging component of the study.

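### The recruitment total of 70 allows for screen failures but for no loss after eligibility, so the power statement at 30 per group has no margin

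*Combined protocol and SAP*

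**What the plan says.** Three statements make up the recruitment count:

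- Section 6a, on completers: "60 total participants will complete baseline assessment, alcohol and placebo sessions (30 diagnosed with bipolar disorder and 30 healthy comparison subjects".
- Section 6a, on screen failures: "We also expect to recruit approximately 10 participants who will not meet inclusion/exclusion criteria following initial clinical assessment". These people are paid for the interview but are not invited to any scan or beverage session.
- Section 6a, on the total: "Total participants to be recruited includes 70 young adults". Section 7 repeats the same split: "recruited are 70 young adults (30 participants with bipolar disorder and 30 typically developing comparison young adults will complete the study".

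Section 8 claims more than 80% power at alpha 0.05 with 30 per group, for a within-subject d of at least 0.5 and a between-group d of at least 0.7. It does not say whether the test is one-sided or two-sided. It closes: "The recruitment of 30 per group through this application ensures adequate power for testing our hypothesis".

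Section 5 describes checks that come after the clinical interview. Urine pregnancy testing and metal screening are repeated before each alcohol or placebo session. Known or suspected metal excludes, and so does a possible pregnancy too early for the test to detect. After a positive pregnancy test on the session day: "The participant will not be allowed to continue with the alcohol/placebo administration sessions". Under the remote pathway in Section 9, the clinical assessments are done online or by phone, so every on-site check falls after the interview.

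**The concern.** The 10 people set aside leave at the interview stage. Every other recruit is counted as completing baseline, alcohol and placebo sessions, so 30 per group is reached only if nobody eligible is lost later, unless someone is added or replaced. Section 8 then treats recruiting 30 per group as analysing 30 per group.

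This matters because the hypotheses concern the alcohol-versus-placebo difference compared between groups. Section 4 tests it through group-by-condition terms, and Section 5 plans the imaging comparison for people who complete both sessions. Someone with only one session adds little to those terms. If completers fall below 30, the stated power and detectable effects no longer describe the study.

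**Working it through.** **Inputs from the plan.** Recruited 70; screen failures about 10; completers 60 (30 + 30); alpha 0.05; between-group d = 0.7; within-subject d = 0.5; claimed power above 80%. The plan gives no loss rate, so 5% to 20% is my assumed range.

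**Step 1: reproduce the total.** Recruits = completers / (1 − loss) + screen failures. With zero loss, 60 / 1 + 10 = 70. The plan's figure is reproduced exactly, and only with zero loss after eligibility.

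**Step 2: reproduce the power at 30 per group.** Power is the chance that a noncentral t variable exceeds the critical value.

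- Between groups: df = 2n − 2 = 58; noncentrality = d√(n/2) = 0.7 × √15 = 2.71. Power is 76.0% two-sided and 85.0% one-sided.
- Within subject, in one group of 30: df = n − 1 = 29; noncentrality = d√n = 0.5 × √30 = 2.74. Power is 75.4% two-sided and 84.8% one-sided.

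The normal approximation gives 77.4% and 78.2% two-sided, also under 80%. The plan's claim is therefore reproduced one-sided but not two-sided. The two-sided effects detectable with 80% power at n = 30 are 0.736 and 0.529, which round to the plan's 0.7 and 0.5.

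**Step 3: apply assumed losses to the 60 eligible,** rounding completers per group down (for example 30 × 0.9 = 27 and 30 × 0.85 = 25.5, taken as 25).

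| Assumed loss | n per group | Two-sided power, d = 0.7 between | Two-sided power, d = 0.5 within | One-sided power, between | One-sided power, within | Detectable d, between | Detectable d, within |
|---|---|---|---|---|---|---|---|
| 0% | 30 | 76.0% | 75.4% | 85.0% | 84.8% | 0.74 | 0.53 |
| 5% | 28 | 73.0% | 72.3% | 82.7% | 82.5% | 0.76 | 0.55 |
| 10% | 27 | 71.4% | 70.6% | 81.4% | 81.2% | 0.78 | 0.56 |
| 15% | 25 | 67.9% | 67.0% | 78.7% | 78.3% | 0.81 | 0.58 |
| 20% | 24 | 66.1% | 65.0% | 77.2% | 76.8% | 0.83 | 0.60 |

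Detectable d is for 80% power at two-sided 0.05.

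**Scope.** These figures use alpha 0.05, as Section 8 does. The connectivity models in Section 4 use 0.004, which is a separate matter.

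**The case against.** The best defence is that 30 per group is a completer target. Power quoted at completers is correct in form, and the 10 is expressly an estimate. A reader might infer that the study cannot reach 30 per group once anyone is lost. The documents do not support that: 70 is nowhere declared a cap, replacement is nowhere forbidden, and fewer than 10 may fail screening. The available text also ends in Section 9 and has no exclusion list, so a replacement rule may exist elsewhere. What stands is that no allowance is stated where the numbers are set out.

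A reader might also count more removal rules than the plan contains:

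- The transport requirement is explained at invitation, so it is mainly a condition of entry. Someone who drove can leave the car overnight or be rescheduled.
- Section 5 says "Subjects can be removed at any time from the scanner by simply requesting to be", but not that this ends participation or rules out another scan.
- Metal is screened at the start as well, so new exclusions at a repeat check should be few, and some could fall among the 10.

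A positive pregnancy test is the one clear removal at the session stage. Nor do the documents give any basis for expecting losses to differ between the groups.

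Finally, attrition is not the main reason the two-sided power is below 80%; that shortfall is present at 30 per group. One-sided, the claim survives a 10% loss. And if the within-subject effect were tested across all 60 participants, two-sided power would be 96.8%, so the missing margin would concern the between-group effect only. Section 8 words the claim per group of 30, which is the reading used here.

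**Conclusion.** The point holds as a missing allowance, not as proof that the target is out of reach. The count balances only with zero loss after eligibility, and the plan itself provides for at least one kind of later removal.

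The size is moderate. A 10% loss raises the two-sided detectable between-group effect from 0.74 to 0.78, and a 20% loss raises it to 0.83. Because two-sided power at the stated effects is already about 75% to 76% at 30 per group, there is no slack to absorb even this. On the one-sided reading the slack runs out between 27 and 25 per group.

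The conclusion rests on simple two-sample and paired t-tests, equal groups, and loss rates that I assumed. It should be corrected, because Section 8 gives an unqualified assurance at a number for which no margin is shown.

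**What to change.** Keep the total at 70 and revise Sections 7 and 8:

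1. List screen failures and losses after eligibility as separate lines.
2. State an assumed loss rate and the expected completers per group under it (for example 27 at 10% or 24 at 20%).
3. State whether the tests are one-sided or two-sided.
4. Quote the detectable effects at the expected number of completers. For two-sided tests with 80% power these are 0.74, 0.78 and 0.83 between groups, and 0.53, 0.56 and 0.60 within subject, at 30, 27 and 24 per group.
5. Replace the closing assurance of adequate power in Section 8 with that statement.
6. Add that screen-failure places not used may go to replacements for non-completers, each taking the same group and beverage order so that the counterbalancing is kept.

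The cost is wording and slightly less favourable stated effects. No added participants or procedures are needed.

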Official title: Subjective Response to Alcohol and Associated Neural Systems in Bipolar Disorder

NCT number: NCT04063384

Document last approval date: 8/28/2023

Document information: Overall study protocol and change in behavior and functional connectivity (primary outcomes) statistical analysis approach.

1 Research Hypothesis

To input text, click in the light grey area below.

We hypothesize that:

- a) Individuals with bipolar disorder will show a low response to alcohol (decreased self-report of feeling intoxicating and experiencing stimulating/sedative effects of alcohol) and a low response to alcohol will be associated with higher alcohol intake.
- b) Individuals with bipolar disorder, compared to healthy comparison subjects, will show smaller alcohol-induced changes in regional responses of, and functional connections between, the amygdala, striatum, and the dorsal and ventral prefrontal and anterior cingulate cortices. Smaller change in regional responses of, and functional connections between, these regions will be associated with a self-reported low level of response to alcohol.

2 Study Background

To input text, click in the light grey area below.

Disease progression in bipolar disorder is very heterogeneous and our understanding of mechanisms associated with differences in disease progression is limited. Bipolar disorder has a high rate of comorbidity with alcohol use disorders (AUDs) [1-3], with estimates as high as 60% [4]. Comorbidity with AUDs is related to more severe illness outcomes in bipolar disorder, including increased impulsive risk-taking [5-8], more severe mood episodes [9, 10], cognitive deficits [11-13], decreased quality of life and a higher risk for suicide [14-17]. These associations highlight the importance of understanding how this comorbidity develops and the relationship with disease progression in bipolar disorder. However, there has been little study in this area; neuroimaging studies in bipolar disorder have not focused on alcohol use, and related differences in disease progression and, in fact, often exclude subjects with this comorbidity from study.

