Group (bipolar, healthy)-by-condition (alcohol, placebo)-by-time of subjective response interactions on subjective response to alcohol will be modeled, covarying beverage condition order, biological sex, and age with SEAS and DEQ subscale scores as the dependent variables. Time of subjective response (pre- and post-scan) and beverage condition (alcohol, placebo) will be within-subject factors and group an independent between-subject factor. Following no group-by-condition-by-time of subjective response interaction, the three-way interaction term will be dropped and group-by-condition interactions investigated. Following no two-way interaction, the two-way interaction term will be dropped and main effects of group and condition assessed. Findings for these planned analyses will be considered significant at $p < 0.05$.

Between Group Differences in Functional Connectivity to Alcohol

Using the CONN Toolbox, we will perform region of interest (ROI)-to-ROI bivariate correlation first-level analysis to calculate fisher transformed correlation coefficients (measure of functional connectivity (FC)) between a priori ROI-to-ROI connections during placebo and alcohol condition CPT-END fMRI sessions. We will extract Fisher transformed correlation coefficients between ROI-to-ROI connections during emotional stimuli and during squares for analysis. We will calculate the contrast: FC during emotional stimuli minus FC during squares for alcohol and placebo conditions, in line with prior studies. A priori ROIs will be defined using the FSL Harvard Oxford Atlas in the CONN toolbox, and included bilateral insula, amygdala, nucleus accumbens (NAcc), ventromedial PFC (vmPFC), lateral orbitofrontal cortex (OFC), subcallosal cortex (SCC), and inferior frontal gyrus pars triangularis (IFG.tri). We will examine ROI-to-ROI connections between limbic/subcortical regions (insula, amygdala, or NAcc) with ventromedial PFC (vmPFC or SCC) and ventrolateral PFC (OFC or IFG.tri) regions.

We will use a mixed model to examine group by condition by hemisphere (left, right) interactions on ROI-to-ROI FC response to emotional stimuli (contrast: emotional stimuli - squares). Group will be an independent between-subject factor, condition and hemisphere within-subject factors, and ROI-to-ROI FC the dependent variable. Results of primary models will be considered significant at $p \leq 0.004$ (Bonferroni correction for twelve ROI-to-ROI connections).

STUDY PROCEDURE DESCRIPTION

5

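### With 30 per group, two-sided t-tests give 75–76% power, not the stated >80%, at within-subject d = 0.5 and between-group d = 0.7; at the connectivity threshold of 0.004 they give 37–40%

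*Combined protocol and SAP*

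**What the plan says.** Section 8 sets alpha at 0.05 and says that "30 subjects per group will provide >80% statistical power to detect a within subject ES" of d ≥ 0.5 and a between-group effect of d ≥ 0.7. It then says the design has enough power for both aims, cites pilot between-group effects "ranging from 0.7 to 1.3; Aim 1a", and concludes: "The recruitment of 30 per group through this application ensures adequate power for testing our hypothesis".

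The 30 per group are completers. Section 6 says "60 total participants will complete baseline assessment, alcohol and placebo sessions", and the 10 further recruits are expected screening failures.

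Section 4 (Data Analysis) sets two thresholds. For the Aim 1 models of subjective response, "Findings for these planned analyses will be considered significant at" p < 0.05. For the functional connectivity models the threshold is p ≤ 0.004, a Bonferroni correction for twelve connections. Neither is described as one-sided or two-sided.

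Section 1 words its hypotheses directionally: bipolar participants "will show smaller alcohol-induced changes in regional responses of" the named brain regions. No section declares a one-sided test.

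**The concern.** A power claim for d at or above a bound has to hold at the bound. Here neither bound gives 80% under the test most readers would assume, and both miss in the same direction. The smallest pilot between-group effect for Aim 1 is d = 0.7, which is exactly the value in question.

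The threshold is a second problem. The sentence is computed at 0.05, yet Section 8 extends its conclusion to both aims. Functional connectivity, which the title page lists among the primary outcomes, is judged at less than a tenth of that alpha. This section is the only sample size justification in the document, so a reader would take it that the connectivity tests have more than 80% power at the quoted effects.

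**Working it through.** **Inputs.** From Sections 6 and 8: n = 30 per group (60 completers), alpha 0.05, within-subject d = 0.5, between-group d = 0.7. From Section 4: alpha 0.004 for connectivity. Assumed here because not stated: two-sided tests without covariates, and within-subject d on the scale of the SD of the differences.

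**Formulas.** Power comes from the noncentral t distribution, with noncentrality δ and two-sided critical value t*.
- Two-sample: δ = d√(n/2), df = 2n − 2.
- Paired: δ = d√n, df = n − 1.

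**Attempt to reproduce >80% at alpha 0.05, two-sided.**
- Between: δ = 0.7 × √15 = 2.711, df = 58, t* = 2.002. Power 76.0%.
- Within: δ = 0.5 × √30 = 2.739, df = 29, t* = 2.045. Power 75.4%.
- The normal approximation, which is slightly optimistic at this n, gives Φ(2.711 − 1.960) = 77.4% and Φ(2.739 − 1.960) = 78.2%. Both remain below 80%.

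Solving the same formulas for d at 80% power gives 0.736 between and 0.529 within. At d = 0.7 and paired d = 0.5, 80% power would need n = 34 in each case.

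**Bases that do exceed 80%, none of them stated.**

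| Basis | Between, d = 0.7 | Within, d = 0.5 |
|---|---|---|
| One-sided alpha 0.05 | 85.0% | 84.8% |
| All 60 pooled, two-sided (δ = 0.5√60, df = 59) | not applicable | 96.8% |
| Three covariates, assumed R² = 0.10 (δ = 2.711/√0.90, df = 55) | 80.2% | not applicable |
| Mean of two repeated measures, assumed correlation 0.7 (δ = 2.711/√0.85) | 82.4% | not applicable |
| Raw-SD d, assumed within-person correlation 0.6 (d becomes 0.5/√0.8 = 0.559) | not applicable | 84.1% |

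The last three depend on the assumed value:
- Covariates reach 80% only from R² of about 0.096.
- A raw-SD d reaches 80% only from a correlation of about 0.55 (at 0.5 it gives 75.4%).
- Averaging two measures gives 80.2% at a correlation of 0.8 and 78.1% at 0.9. It helps a main effect of group measured on the single-observation SD scale, not an interaction.

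**At the connectivity threshold, alpha 0.004, two-sided.**
- Between: δ = 2.711, df = 58, t* = 2.998. Power 39.6%.
- Within: δ = 2.739, df = 29, t* = 3.127. Power 36.9%.
- Within, all 60 pooled: 80.5%.

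Solving for d at 80% power with 30 per group gives about 1.00 between and 0.73 within.

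**The case against.** The strongest reply is that Section 8 never says two-sided. Its hypotheses are directional, and a one-sided 0.05 test gives about 85% for both effects. The planned models also use covariates and repeated measures, which can add precision that a simple t-test ignores. And 0.736 and 0.529 round to 0.7 and 0.5 at one decimal, so the sentence may be a correct calculation with rounded effect sizes. That last explanation is inference, but it fits both figures.

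Much of this stands. A reader might infer that >80% is a plain miscalculation. The documents do not support that, because they omit the test, the sidedness and the scale, and several reasonable bases reach the figure. What remains is that none of those bases is stated. Directional hypotheses do not declare a one-sided test, and Section 8 credits no gain from covariates or repeated measures. As printed, the figure fails under the usual default.

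A reader might also infer that the pilot range of N = 3 to N = 29 is an error. It gives no power level, test, or per-group or total basis, so it cannot be checked. That is a gap in reporting, not a demonstrated mistake.

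On materiality, the 4 to 5 point gap affects only the bottom of the quoted effect range; larger pilot effects are unaffected. This reply does not cover the 0.004 threshold. Pooling all 60 would bring the within-subject effect to 80.5% there, but the Section 1 connectivity hypothesis is a comparison between groups.

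**Conclusion.** The point holds in a limited form. With two-sided t-tests at alpha 0.05, 30 per group gives 76.0% power at between-group d = 0.7 and 75.4% at paired d = 0.5, against a stated >80%. The figure needs an assumption the documents do not supply. This rests on no covariate gain and on d scaled by the SD of the differences for the within-subject test.

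The claim of adequate power for both aims is not supported by a calculation at 0.05, because connectivity is judged at 0.004. At the quoted effects, simple t-tests there give about 40% and 37%. These are not the power of the planned mixed models, which depends on variances and correlations that are not given. They show only that the 0.05 statement does not carry over.

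Nor does it follow that the trial must enrol more people. The gap at 0.05 is small, and Section 8 gives no pilot estimate of the between-group difference in connectivity change from which to judge power at 0.004.

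**What to change.** In Section 8, do one of the following:
- State that 30 completers per group give 80% power for a between-group d of at least 0.74 and a within-group d of at least 0.53, at two-sided alpha 0.05, using simple t-tests as an approximation to the planned models; or
- Keep >80% and name the basis that produces it, with the assumed value (one-sided testing, pooling of all 60, covariate R², number and correlation of repeated measures, or scale of d and within-person correlation).

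In either case, say that the statement covers single tests at 0.05. Then either add the power or detectable effect at 0.004 (on the same approximation, d of about 1.00 between and 0.73 within for 80%) or remove the claim that both aims are sufficiently powered.

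The cost is protocol wording, and stated power that looks less favourable unless a valid basis is named. Enrolment and the planned analyses do not change.

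### Section 8's claim of more than 80% power at a between-group d of 0.7 is 76% for a two-sided test, and it does not carry over to the three-way interaction that opens Aim 1

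*Combined protocol and SAP*

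**What the plan says.** Section 8 (Sample size rationale) sets the error rate with "At an alpha=0.05" and states that "30 subjects per group will provide >80% statistical power to detect a within subject ES $d \geq 0.5$ and a between group ES $d \geq" (the value given is 0.7). It supports this with pilot results: "we observed large between group ESs when comparing differences in subjective response to alcohol (with Cohen's d ranging from 0.7 to 1.3; Aim 1a"). It then concludes that the design has enough power for both aims. The 30 per group are completers: "30 participants with bipolar disorder and 30 typically developing comparison young adults will complete the study" (Section 7).

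Section 4 (Data Analysis, Aim 1) sets out a step-down analysis of the SEAS and DEQ subscales. It starts with the highest-order term: "Group (bipolar, healthy)-by-condition (alcohol, placebo)-by-time of subjective response interactions on subjective response to alcohol will be modeled". If that term is absent it is dropped and group-by-condition is tested, then main effects. The criterion is "Findings for these planned analyses will be considered significant at $p < 0.05". Neither section states sidedness.

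The two levels of time are before and after the scan. Under Laboratory Alcohol Challenge Procedures in Section 5, the first rating is taken once breath alcohol reaches 0.06% on the way up, and the second after a scan of about 30 minutes. Both ratings therefore follow drinking. Hypothesis (a) in Section 1 predicts a low response to alcohol in bipolar disorder and does not predict a change in that response across the scan.

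**The concern.** There are two gaps between the power statement and the analysis.

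First, the stated power is not what a two-sided test delivers at the stated effect and sample size.

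Second, "a between group ES $d \geq 0.7" describes a difference between two groups on one quantity per person, whereas the first Aim 1 test is a contrast of four ratings per person. It asks whether the group difference in alcohol-minus-placebo response changes from the first rating to the second. Its power depends on how the group difference is distributed over the two ratings and on the correlation between ratings. Section 8 gives neither, nor any effect size for an interaction.

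The stake is interpretation. Under the step-down rule, a non-significant three-way term leads to its removal. Beside a general statement of adequate power, a reader could take that result as evidence that the group difference is constant over time, which the design has not been shown able to establish.

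**Working it through.** **Inputs from the documents:** n = 30 per group, alpha = 0.05, d = 0.7 (Section 8); the factors group, condition and time (Section 4).

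**Assumptions, not in the documents:** two-sided tests; unit SD for each rating; equal correlation rho among a person's four ratings; no group difference under placebo. Order, sex and age are left out: entered as main effects, they are constant within a person and cancel from both within-person contrasts below.

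**Step 1: the plan's own figure.** Two-sample t-test with 58 degrees of freedom and noncentrality d × √(n/2) = 0.7 × √15 = 2.71.

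- Two-sided: 76.0% (77.4% by the normal approximation).
- One-sided: 85.0%.
- Two-sided d detectable with 80% power: 0.736, or about 0.74.

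The claim of more than 80% holds only if the test is one-sided, or if 0.74 was rounded to 0.7.

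**Step 2: the three-way contrast.** For each person, C3 = (A1 − A2) − (P1 − P2), where A and P are the alcohol and placebo ratings and 1 and 2 are before and after the scan. Its variance is 4(1 − rho). If the group difference under alcohol changes by Δ between ratings, the standardised effect is Δ / (2√(1 − rho)), tested with 58 degrees of freedom.

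- Difference of 0.7 at one rating only: Δ = 0.7. At rho = 0.5, 0.7 / 1.414 = 0.495.
- Difference of 0.7 falling to 0.35: Δ = 0.35. At rho = 0.5, 0.35 / 1.414 = 0.247.
- Equal difference at both ratings: Δ = 0. There is no effect to detect, and the rejection rate is the 5% type I error rate.

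| rho | Power, Δ = 0.7 | Power, Δ = 0.35 |
|---|---|---|
| 0 | 27% | 10% |
| 0.5 | 47% | 16% |
| 0.7 | 68% | 23% |
| 0.8 | 85% | 32% |

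With Δ = 0.7, power passes 80% at rho of about 0.77: 1 − (0.7 / (2 × 0.736))² = 0.77. Simulation with 10,000 runs at each value gave 46%, 68% and 84% at rho 0.5, 0.7 and 0.8.

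**Step 3: the group-by-condition contrast.** C2 = (A1 + A2)/2 − (P1 + P2)/2 has variance 1 − rho. With a 0.7 SD difference under alcohol at both ratings:

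- rho = 0: d = 0.70, power 76%.
- rho = 0.5: d = 0.7 / √0.5 = 0.99, power 96%.

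**Step 4: unequal correlations.** Suppose the correlation is 0.8 within a session and 0.3 between sessions.

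- Three-way: the between-session covariances cancel, so the variance is 4(1 − 0.8) = 0.8. For Δ = 0.7, d = 0.7 / √0.8 = 0.78 and power is 85%.
- Group-by-condition: each session mean has variance (1 + 0.8)/2 = 0.9, so the contrast variance is 2(0.9 − 0.3) = 1.2. Then d = 0.7 / √1.2 = 0.64 and power is 68%.

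The order of the two tests can therefore reverse, depending on a correlation structure that the plan does not state.

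**The case against.** The strongest reply has three parts.

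First, the correlation between ratings given by the same person before and after one scan may well be 0.7 to 0.8, and at 0.8 the three-way test has 85% power for an effect confined to one rating. Second, 0.7 is the bottom of the pilot range: at rho = 0.5 an effect at one rating only of 1.0 or 1.3 gives 77% or 94%. The plan also does not say how the pilot d was computed; if 0.7 is already in SDs of the three-way contrast, power is 76%. Third, the adequacy statement concerns aims, not individual terms, and the low response in hypothesis (a) can be tested through group-by-condition.

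All three stand, and they limit the point. A reader might infer that three-way power cannot exceed about 47%, that the adequacy statement is false for that term, or that Aim 1 is underpowered. The documents support none of these. The 47% is only the value at an assumed rho of 0.5. The 5% for an equal difference is a type I error rate, not low power against a real three-way effect. And the step-down goes on to a test that can have high power. The plan also nowhere says that a non-significant three-way term will be read as constancy over time; that is a risk of interpretation, not a stated intention.

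The reply does not answer two things: the two-sided figure is 76%, and nothing in Section 8 links d = 0.7 to any contrast in Section 4.

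**Conclusion.** The point holds in two parts. The stated power of more than 80% at d = 0.7 is 76% with a two-sided t-test at 0.05; this assumes only two-sided testing and 30 completers per group. Separately, adequate power for the group-by-condition-by-time term is undemonstrated, not disproved. For a 0.7 SD group difference under alcohol at one rating only, power runs from about 27% to 85% as an assumed common rho goes from 0 to 0.8. If the difference halves across the scan, it is about 10% to 32% over the same range. If the low response is the same at both ratings, as hypothesis (a) allows, the three-way test cannot detect it at any rho. The correction is cheap and worth making, because the plan states a power that the design does not deliver with two-sided tests.

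**What to change.** In Section 8:

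1. Restate the between-group figure for a two-sided test at 0.05 with 30 per group: about 76% power at d = 0.7, or 80% power at d of about 0.74.
2. Name the Aim 1 test that it refers to: the group-by-condition contrast (alcohol minus placebo, averaged over the two ratings), with d in SDs of that contrast. Tying d = 0.7 to this contrast without restating the power would leave the unreproduced figure in place, since d = 0.7 on that scale is again 76%.
3. Limit the adequacy statement for Aim 1 to that contrast, report three-way power over a stated range of rho (the table above would serve), and add that a non-significant three-way term is not evidence that the group difference is constant over time.

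The cost is a few sentences, and a stated power that is slightly less favourable. Enrolment and data collection do not change.
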